## 7.0 STATISTICAL ANALYSIS PLAN

We will simultaneously monitor efficacy and toxicity using the Bayesian optimal phase 2 (BOP2) design (Zhou, Lee and Yuan, 2017). Specifically, let  $n$  denote the interim sample size, and  $N$  denote the maximum sample size. Let  $Y_{eff}$  and  $Y_{tox}$  denote the binary efficacy and toxicity endpoints, with  $Y_{eff} = 1$  and  $Y_{tox} = 1$  indicating that patients experience efficacy and toxicity, respectively. We assume that the joint distribution of  $(Y_{eff}, Y_{tox})$  follows a multinomial distribution with four elementary outcomes:  $(Y_{eff}, Y_{tox}) = (1, 1), (1, 0), (0, 1)$  and  $(0, 0)$ . Let  $\mathbf{p} = (P_{11}, P_{10}, P_{01}, P_{00})$  denote the probabilities of observing the four outcomes, and let  $p_{eff} = Pr(Y_{eff} = 1)$ ,  $p_{tox} = Pr(Y_{tox} = 1)$  and  $p_{eff,tox} = Pr(Y_{eff} = 1, Y_{tox} = 1)$ . When efficacy and toxicity endpoints are monitored separately, the joint distribution reduced to marginal distribution of efficacy and marginal distribution of toxicity, respectively. For trial monitoring and decisions, extreme toxicities (TOX) will be defined as any grade 3 or higher adverse event that is possibly, probably, or related to therapy received on this protocol. Any grade 3 or higher adverse event that is potentially treatable with steroids or hormonal replacement will only count as an extreme toxicity if it does not improve to grade 1 or better within 2 weeks of therapy.

The treatment is deemed unacceptable if  $p_{eff} \leq 0.23$  or  $p_{tox} > 0.5$ . Thus, we will stop enrolling patients and claim that the treatment is unacceptable if

$$Pr(p_{eff} > 0.23 | data) < \lambda \left( \frac{n}{N} \right)^\alpha,$$

or

$$Pr(p_{tox} \leq 0.5 | data) < \lambda \left( \frac{n}{N} \right)^{\alpha/3},$$

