where  $\lambda=0.5$  and  $\alpha=1$  are design parameters optimized to maximize the study power, i.e., probability of correctly concluding an efficacious and safe treatment as acceptable when  $p_{eff} = 0.3$ ,  $p_{tox} = 0.3$  and  $p_{efftox} = 0.18$ , while controlling that the probability of incorrectly claiming an inefficacious and toxic treatment, i.e., type I error, with  $p_{eff} = 0.23$ ,  $p_{tox} = 0.5$  and  $p_{efftox} = 0.15$ , to 9.5%. Note that in the safety stopping rule, the original publication of the design used the probability cutoff  $\lambda(n/N)^\alpha$ , here the attenuation factor 3 is added (i.e.,  $\alpha/3$ ) to obtain stricter interim stopping boundaries to enhance safety.

For the purposes of interim monitoring, toxicities and responses will be monitored for 24 weeks post start of the combination therapy.

This optimization is performed assuming a vague Dirichlet prior  $Dir(0.15, 0.08, 0.35, 0.42)$  for  $\mathbf{p}$ . The prior is chosen such that it corresponds to a prior effective sample size of 1 patient, and the prior estimates of  $p_{eff}$  and  $p_{tox}$  match the values specified when the treatment is unacceptable. The above decision rule leads to the following optimal stopping boundaries:

*Table 1: Optimized stopping boundaries*

# patients treated	Stop if # response <=	OR # toxicity	
		<=	>=
10	0	6	
20	3	11	
35	7	18	
50	11	25	

When the total number of patients reaches the maximum sample size of 50, we conclude that the treatment is acceptable if the number of responses are greater than 11, and the number of toxicities are less than 25; otherwise we conclude that the treatment is unacceptable. The go/no-go criteria in Table 1 are non-binding.

Below are the operating characteristics of the design based on 10000 simulations using the BOP2 web application (BOP2 V1.4.7.0), which is available at <http://www.trialdesign.org>.

*Table 2: Operating characteristics*

Scenario	Pr(Eff)	Pr(Tox)	Pr(Eff & Tox)	Early Stopping (%)	Claim Acceptable (%)	Average Sample Size
1	0.23	0.5	0.15	83.15	9.47	23.0
2	0.30	0.3	0.18	24.46	71.38	42.9

ORR will be summarized with a 95% confidence interval (Clopper-Pearson exact method).

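### The strict inequality in the Section 7.0 toxicity rule does not reproduce the plan's own final toxicity boundary of 25 of 50; the two meet at an exact tie, and the inequality should admit it

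*Combined protocol and SAP*

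**What the plan says.** Section 7.0 gives two stopping inequalities, one for efficacy and one for toxicity, introduced by "Thus, we will stop enrolling patients and claim that the treatment is unacceptable if". The toxicity inequality compares Pr(p_tox ≤ 0.5 | data) with λ(n/N)^(α/3), using a strict less-than sign. The design parameters are λ = 0.5 and α = 1. The prior is Dirichlet with parameters 0.15, 0.08, 0.35 and 0.42.

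The plan then states: "The above decision rule leads to the following optimal stopping boundaries". Table 1 of that section (optimized stopping boundaries) has looks at 10, 20, 35 and 50 patients. Its final toxicity boundary is 25.

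The final decision also has its own sentence, which begins "When the total number of patients reaches the maximum sample size of 50". The treatment is acceptable if "the number of responses are greater than 11" and "the number of toxicities are less than 25", and otherwise unacceptable. The type I error is given as 9.5% in the text and 9.47% in Table 2 of Section 7.0, from 10,000 simulations.

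**The concern.** The plan presents Table 1 as a consequence of the inequalities, so each boundary should follow from them. The final toxicity boundary does not. If the trial reaches 50 patients with exactly 25 toxicities and more than 11 responses, the printed formula leads to acceptable, while the table and the sentence lead to unacceptable.

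What is at stake is the final classification in that single case, and whether the printed formula carries the type I error quoted for the design. A pre-specified plan should not leave a choice between formula and table to be made once the data are known.

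**Working it through.** **Inputs (all from Section 7.0).** λ = 0.5; α = 1, so the toxicity exponent is 1/3; N = 50; looks at 10, 20, 35 and 50; prior Dir(0.15, 0.08, 0.35, 0.42) for the outcomes (response and toxicity, response only, toxicity only, neither).

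**Marginal priors.** For p_eff: 0.15 + 0.08 = 0.23 and 0.35 + 0.42 = 0.77, giving Beta(0.23, 0.77). For p_tox: 0.15 + 0.35 = 0.5 and 0.08 + 0.42 = 0.5, giving Beta(0.5, 0.5). After x events in n patients the posteriors are Beta(0.23 + x, 0.77 + n − x) and Beta(0.5 + x, 0.5 + n − x).

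**Efficacy: stop if Pr(p_eff > 0.23) < 0.5(n/50).**

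| n | Cutoff | Largest count that stops | Next count, does not stop | Table 1 |
|---|---|---|---|---|
| 10 | 0.100 | 0 (0.006) | 1 (0.111) | 0 |
| 20 | 0.200 | 3 (0.160) | 4 (0.337) | 3 |
| 35 | 0.350 | 7 (0.308) | 8 (0.463) | 7 |
| 50 | 0.500 | 11 (0.409) | 12 (0.543) | 11 |

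**Toxicity: stop if Pr(p_tox ≤ 0.5) < 0.5(n/50)^(1/3).**

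| n | Cutoff | Largest count that does not stop | Smallest count that stops | Table 1 |
|---|---|---|---|---|
| 10 | 0.292 | 5 (0.500) | 6 (0.265) | 6 |
| 20 | 0.368 | 10 (0.500) | 11 (0.328) | 11 |
| 35 | 0.444 | 17 (0.567) | 18 (0.433) | 18 |
| 50 | 0.500 | 25 (0.500, tie) | 26 (0.389) | **25** |

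Posterior probabilities are in parentheses. Seven of the eight boundaries reproduce, which confirms the reading of the prior, λ, α and the attenuation factor 3. The eighth does not. At n = N the cutoff is 0.5 × 1 = 0.5 whatever the exponent. With 25 of 50 the posterior Beta(25.5, 25.5) is symmetric about 0.5, so the probability is exactly 0.5, and 0.5 < 0.5 is false. With ≤ in place of < the boundary is 25. None of the first three toxicity boundaries is a tie with its cutoff, so that change moves nothing else.

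**Operating characteristics.** These come from an exact recursion over the joint counts of responses and toxicities. The null scenario is (p_eff, p_tox, p_efftox) = (0.23, 0.5, 0.15) and the target scenario is (0.30, 0.3, 0.18).

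| | Table 2 (simulated) | Exact, boundary 25 | Exact, boundary 26 |
|---|---|---|---|
| Null: claim acceptable | 9.47% | 9.56% | 10.93% |
| Null: early stopping | 83.15% | 83.40% | 83.40% |
| Null: average sample size | 23.0 | 22.96 | 22.96 |
| Target: claim acceptable | 71.38% | 71.91% | 71.96% |
| Target: early stopping | 24.46% | 23.79% | 23.79% |
| Target: average sample size | 42.9 | 43.12 | 43.12 |

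The Monte Carlo standard error of 9.47% with 10,000 runs is √(0.0947 × 0.9053 / 10,000) = 0.29 points. Boundary 25 lies 0.09 points from Table 2, well within that error. Boundary 26 lies 10.93 − 9.47 = 1.46 points away, about five standard errors. Table 2 therefore describes boundary 25.

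**Size of the disputed outcome.** The two boundaries differ only when the trial ends with exactly 25 toxicities and more than 11 responses. From the unrounded values, that has probability 10.934 − 9.556 = 1.38% under the null and 71.957 − 71.913 = 0.04% under the target scenario.

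**The case against.** The strongest reply is that the operative text is already clear. Section 7.0 defines n as the interim sample size and words the inequality as a rule to stop enrolling, and at 50 patients there is no enrolment left to stop. The final decision has its own explicit sentence, and Table 1 repeats the number. Staff will use the table, not a beta integral. The criteria are also declared non-binding, and 25 is the stricter of the two boundaries for safety.

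Most of this stands, and it is why the point is minor. It does not remove the mismatch. The plan says the rule leads to Table 1, and that table includes the row for 50. The final efficacy boundary of 11 does follow from the same pair of inequalities at n = 50, so they are being applied at the last look. That the criteria are non-binding does not settle which rule the quoted operating characteristics describe.

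A second reply is that software comparing floating-point numbers may return 25 even with a strict sign. That depends on the package. At this tie scipy returns 0.4999999999999989, which would stop, and R returns 0.50000000000000011, which would not. The documents do not say how the web application arrived at 25, so rounding is only a possible explanation. The dependence on software is itself a reason to write the tie explicitly.

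**Conclusion.** The printed toxicity inequality and the printed final toxicity boundary disagree at one exact tie, 25 toxicities in 50 patients. Followed literally, the formula gives 26 and a type I error of 10.9%.

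A reader might infer that the plan misreports its type I error, or that 25 is a computing mistake. The documents do not support either inference. Table 1, the final-decision sentence and the 9.5% agree with one another, and Table 2 matches them within simulation error. The 10.9% belongs to a boundary that the plan nowhere prints. What is wrong is the inequality sign.

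No interim boundary, early-stopping probability or average sample size is affected, and power differs by about 0.04 points. The result rests on the stated prior, λ, α and four looks, and on type I error meaning acceptance under the plan's joint null scenario. Severity: minor, limited to one outcome at the final look.

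**What to change.** Reconcile the formula with the table in one of two ways:

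- replace < with ≤ in the toxicity inequality of Section 7.0; or
- keep the formula and add a sentence saying that Table 1 of that section governs and that a tie counts as meeting the boundary.

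Either way the formula, table, final-decision sentence and 9.5% agree. The cost is one symbol or one sentence. No simulation needs repeating, and the other seven boundaries, Table 2 and the sample size stay as printed. The edit should be made before the final toxicity count is known.

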## **5.9 Clinical Criteria for Early Trial Termination**

Early trial termination will be the result of the criteria specified below:

1. Quality or quantity of data recording is inaccurate or incomplete
2. Poor adherence to protocol and regulatory requirements
3. Incidence or severity of adverse drug reaction in this or other studies indicates a potential health hazard to participants
4. Plans to modify or discontinue the development of the study drug

In the event of Merck decision to no longer supply study drug, adequate notification will be provided so that appropriate adjustments to participant treatment can be made.

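### Table 1 is called non-binding, but the stated 9.5% type I error holds only if crossing an interim boundary still forfeits the 'acceptable' claim

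*Combined protocol and SAP*

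**What the plan says.** Section 7.0 sets out a BOP2 design with looks at 10, 20, 35 and 50 patients. When either posterior criterion is met, "we will stop enrolling patients and claim that the treatment is unacceptable if" introduces the consequence. That consequence has two parts: an action on enrolment and a conclusion about the treatment.

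Below Table 1, the final rule at 50 patients requires that "the number of responses are greater than 11, and the number of toxicities are less than 25" before an acceptable conclusion is drawn. For any other final result it says "otherwise we conclude that the treatment is unacceptable". The statement that follows this rule reads "The go/no-go criteria in Table 1 are non-binding".

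The design parameters are said to be chosen to maximise power while "controlling that the probability of incorrectly claiming an inefficacious and toxic treatment, i.e., type I error" to 9.5%. Table 2 reports one set of operating characteristics, introduced by "Below are the operating characteristics of the design based on 10000 simulations using the BOP2 web application". At the joint null it gives 9.47% acceptable, 83.15% early stopping and an average sample size of 23.0. At the alternative it gives 71.38%, 24.46% and 42.9.

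**The concern.** The sentence on non-binding criteria does not say which part of the consequence is relaxed. If only the enrolment action is discretionary, a trial that crosses a boundary and continues has still lost its claim, and the stated error rate stands. If the conclusion is discretionary too, a trial can cross at 10, 20 or 35 patients, run to 50, finish with for example 12 responses and 24 toxicities, and be called acceptable under the final rule. The earlier sentence would call the same trial unacceptable.

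At stake is the main go/no-go conclusion and the error rate attached to it. The stated 9.5% takes full credit for interim stops that the plan then makes optional. The trial is open label, so if the rule is left open, whether a crossing counted could be decided after the counts are known.

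**Working it through.** **Inputs, all from Section 7.0.**
- Interim boundaries (Table 1): responses ≤ 0, 3, 7 or toxicities ≥ 6, 11, 18 at n = 10, 20, 35.
- Final rule: more than 11 responses and fewer than 25 toxicities at n = 50.
- Joint null: p_eff 0.23, p_tox 0.50, both 0.15. The cell probabilities are p11 = 0.15, p10 = 0.23 − 0.15 = 0.08, p01 = 0.50 − 0.15 = 0.35, p00 = 0.42.
- Alternative: 0.30, 0.30, 0.18. The cells are 0.18, 0.12, 0.12, 0.58.

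**Method.** The joint distribution of responses r and toxicities t is carried forward exactly, one patient at a time:

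D(r,t) ← p00·D(r,t) + p10·D(r−1,t) + p01·D(r,t−1) + p11·D(r−1,t−1).

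At each interim look, the probability in the crossing region is removed (crossing forfeits the claim), kept (crossing ignored), or kept in proportion q (each crossing overridden with probability q, applied afresh at each look). What remains at n = 50 and meets the final rule is the probability of claiming acceptable.

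**Step 1: reproduce Table 2, with every interim boundary applied.**

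| | Acceptable | Early stop | Average N |
|---|---|---|---|
| Joint null, exact | 9.56% | 83.40% | 22.96 |
| Joint null, plan | 9.47% | 83.15% | 23.0 |
| Alternative, exact | 71.91% | 23.79% | 43.1 |
| Alternative, plan | 71.38% | 24.46% | 42.9 |

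With 10,000 runs, the simulation standard error of the null acceptance rate is √(0.0947 × 0.9053 / 10000) = 0.29 points. For the alternative it is √(0.7138 × 0.2862 / 10000) = 0.45 points. The gaps are 0.09/0.29 ≈ 0.3 and 0.53/0.45 ≈ 1.2 standard errors, and every Table 2 percentage is within about 1.6. Table 2 therefore assumes that every boundary is applied. Its acceptance rates need only forfeiture of the claim; its early-stopping rates and average sample sizes also need enrolment to stop.

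**Step 2: let crossings be overridden and the 50-patient rule decide.**

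| Crossings ignored | Type I error, joint null | Power |
|---|---|---|
| None | 9.6% | 71.9% |
| Futility at one look (n = 10, 20, 35) | 9.7%, 10.3%, 10.5% | within 72.1–75.2% |
| Toxicity at one look (n = 10, 20, 35) | 11.1%, 10.3%, 10.5% | within 72.1–75.2% |
| Each with probability 10% (assumed) | 10.1% | 73.0% |
| Each with probability 25% (assumed) | 11.0% | 74.7% |
| All futility crossings | 12.2% | 80.6% |
| All toxicity crossings | 15.3% | 77.0% |
| Every crossing (bound; N = 50) | 19.0% | 85.9% |

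**Step 3: size of the undefined outcome at the bound.** With no interim stop, the share of trials that cross and still meet the final rule is 18.98 − 9.56 ≈ 9.4 points at the joint null and 85.86 − 71.91 ≈ 13.95 points at the alternative. These shares assume that every crossing is ignored.

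**The case against.** The best defence is that Section 7.0 already supplies the answer. The consequence of a crossing is stated without qualification and includes the unacceptable claim. The final rule applies when 50 patients are reached, which under that consequence happens only if nothing was crossed. On this view, non-binding means ordinary discretion over enrolment. Table 2's early-stopping column also shows that stopping was enforced in the simulation. This is a reasonable reading, and under it 9.5% stands. But the text does not exclude the other reading, and the final rule carries no condition about earlier looks.

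The size can also be overstated, and three stronger inferences fail:
- **That the true type I error is 19%.** That figure requires ignoring every crossing, which at the joint null means overriding stops in 83% of trials. It is a bound, and the documents give no override rate.
- **That crossing and then passing is a common path.** The 9.4 and 13.95 points rest on the same extreme assumption. Section 5.9 also has a separate ground for termination, "Incidence or severity of adverse drug reaction in this or other studies indicates a potential health hazard to participants", which makes routine overriding of toxicity boundaries less likely.
- **That the 71% power is unsupported.** Overriding a stop can only add acceptable conclusions, so 71% is a lower bound.

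It is also fair that this is a single-arm phase II trial whose response rate will be reported with an exact interval whatever the go/no-go label. That limits the consequence but does not settle the rule.

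**Conclusion.** The point holds as an unresolved conflict within Section 7.0 that bears on the type I error only. The stated 9.5% is correct if any interim crossing forfeits the acceptable claim, whether or not enrolment continues, and the plan does not say so. If crossings may be overridden, the rate exceeds 9.5%. Limited overriding adds a modest amount (9.7–11.1% for one endpoint at one look; 10.1% or 11.0% at the assumed 10% or 25% override probabilities), and 19.0% is the ceiling.

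The figures assume the Table 1 boundaries as printed, complete outcome data at each look, and the 50-patient rule applied as written. They refer to the joint null (0.23/0.50/0.15) only; how the design behaves when just one endpoint is at its null value is a separate question.

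One related gap remains. Table 1 has a row for 50 patients, so the non-binding sentence literally reaches the final rule as well, although the prose states that rule as definite. It should be fixed because the error rate attached to the trial's main conclusion depends on it and the remedy is very small.

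**What to change.** Reconcile the two statements in Section 7.0 in one of two ways.

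(a) Add a sentence such as: *Crossing any interim boundary in Table 1 rules out an acceptable conclusion, whether or not enrolment continues.* This keeps the type I error at about 9.5% at the joint null and power at about 71%. Note beside Table 2 that its early-stopping rates and average sample sizes assume that enrolment stops at a crossing.

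(b) Keep the interim criteria non-binding, label Table 2 as conditional on adherence to the interim boundaries, and add the no-interim-stop values: 19.0% acceptable at the joint null and 85.9% at the alternative, with N = 50. Mark these as an upper bound.

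In both cases, state that the conclusion rule at 50 patients is binding.

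Whether enrolment or treatment continues after a crossing is for the sponsor to reconcile between the stopping sentence and the non-binding sentence; this point takes no position on it.

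The cost is one or two sentences, plus a label and two rows in Table 2 under (b). Boundaries, sample size, visits and procedures do not change.

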## **8.0 LABELING, PACKAGING, STORAGE AND RETURN OF CLINICAL SUPPLIES**

### **8.1 Investigational Product**

The investigator shall take responsibility for and shall take all steps to maintain appropriate records and ensure appropriate supply, storage, handling, distribution and usage of investigational product in accordance with the protocol and any applicable laws and regulations.

Pembrolizumab will be provided by Merck as summarized in Table 10.

**Table 10 Product Descriptions**

Product Name & Potency	Dosage Form
Pembrolizumab 100 mg/ 4mL	Solution for Injection

### **8.2 Packaging and Labeling Information**

Supplies will be labeled in accordance with regulatory requirements.

### **8.3 Clinical Supplies Disclosure**

This trial is open-label; therefore, the participant, the trial site personnel, the Sponsor and/or designee are not blinded to treatment. Drug identity (name, strength) is included in the label text; random code/disclosure envelopes or lists are not provided.

### **8.4 Storage and Handling Requirements**

Clinical supplies must be stored in a secure, limited-access location under the storage conditions specified on the label.

Receipt and dispensing of trial medication must be recorded by an authorized person at the trial site.

Clinical supplies may not be used for any purpose other than that stated in the protocol.

## **8.5 Returns and Reconciliation**

The investigator is responsible for keeping accurate records of the clinical supplies received from Merck or designee, the amount dispensed to and returned by the participants and the amount remaining at the conclusion of the trial.

Upon completion or termination of the study, all unused and/or partially used investigational product will be destroyed at the site per institutional policy. It is the Investigator's responsibility to arrange for disposal of all empty containers, provided that procedures for proper disposal have been established according to applicable federal, state, local and institutional guidelines and procedures, and provided that appropriate records of disposal are kept.

## **9.0 ADMINISTRATIVE AND REGULATORY DETAILS**

## **10.0 REFERENCES**

At the end of protocol

## 11.0 APPENDICES

### Appendix 1: ECOG Performance Status

Grade	Description
0	Normal activity. Fully active, able to carry on all pre-disease performance without restriction.
1	Symptoms, but ambulatory. Restricted in physically strenuous activity, but ambulatory and able to carry out work of a light or sedentary nature (e.g., light housework, office work).
2	In bed <50% of the time. Ambulatory and capable of all self-care, but unable to carry out any work activities. Up and about more than 50% of waking hours.
3	In bed >50% of the time. Capable of only limited self-care, confined to bed or chair more than 50% of waking hours.
4	100% bedridden. Completely disabled. Cannot carry on any self-care. Totally confined to bed or chair.
5	Dead.

\* As published in Am. J. Clin. Oncol.: *Oken, M.M., Creech, R.H., Tormey, D.C., Horton, J., Davis, T.E., McFadden, E.T., Carbone, P.P.: Toxicity And Response Criteria Of The Eastern Cooperative Oncology Group. Am J Clin Oncol 5:649-655, 1982.* The Eastern Cooperative Oncology Group, Robert Comis M.D., Group Chair.

